### **Unanticipated Adverse Device Effect (UADE)**

An unanticipated adverse device effect (UADE) is not expected to occur. An UADE is defined as any serious adverse effect on health or safety or any life-threatening problem or death caused by – or associated with – the device, if that effect, problem, or death was not previously identified in nature, severity, or degree of incidence in the investigational plan (including documents such as the protocol, the informed consent document, other study-related documents), or any other unanticipated serious problem associated with the device that relates to the rights, safety, or welfare of participants.

During the review of a reported SAE, if the Investigator determines the severity or extent of the event was not cited in this protocol or associated protocol materials, and the event was classified as, “possibly related” to the device, the event will be documented as an UADE. If the event is classified as an UADE, the Investigator must notify the IRB and FDA within ten (10) working days of the original SAE notification.

If determined that the UADE presents an unreasonable risk to participants, the investigators will terminate all investigations or parts of investigations presenting that risk as soon as possible, but not later than five working days after such determination is made and not later than 15 working days after first notice of the original SAE. A terminated study will not be resumed without IRB and FDA approval.

## Medical Device Reporting (MDR) Events

A device issue, whether related to a complaint or not, is an allegation from the participant or study personnel regarding an indication of the failure of a device to meet user expectations for quality or performance specifications. Device issues will be recorded onto appropriate CRFs by site personnel. For purposes of this protocol, the CGM device is currently marketed. Therefore, the investigator will follow the required reporting regulations if an MDR reportable event occurs, according to standard operating procedures and FDA guidelines. (US MDR Reporting; Code of Federal Regulations Title 21 Part 803).

MDR reportable events are events that manufacturers become aware of that reasonably suggest one of their marketed devices may have caused or contributed to a death or serious injury or has malfunctioned and the malfunction of the device would likely cause or contribute to a death or serious injury if the malfunction were to recur (21 CFR 803.3).

## Adverse event reporting

Hypo- and hyperglycemia will not be considered AEs unless the subject has positive ketones of 1.2 mM or displays symptoms of hypoglycemia such as: loss of consciousness, slurred speech, hospitalization, or EMS services called. Disease related events that are chronic in nature and occur as part of the progression of the diabetes disease state (i.e., diagnoses of retinopathy, nephropathy, and neuropathy) will not be captured as AEs in this study.

One of the investigators will write up a description of the adverse event/unanticipated problem. All reportable new information (RNI) will be reported to the IRB within five calendar days after the PI learns of the event. RNI is any information that might meet the regulatory definition of an unanticipated problem involving risks to participants or others or serious or continuing noncompliance that might impact the criteria for IRB approval.

The report will be submitted to the IRB by the principal investigator or study coordinator. A summary of all UPs and adverse events, including those that do not meet the requirement for RNI, will be submitted with the continuing review. The FDA will be notified of any unanticipated adverse event related to the use of the study device. Notification will be made within 10 days after the Principal Investigator becomes aware of the event. Any SAE, including death, due to any cause (related or unrelated to devices), that may occur during a clinical study will be reported immediately (within 1 working day of learning of the event).

### **Missing data**

Participants who contribute at least 14 nights plus 24 hours following bedtime in at least one of the study conditions will be included in the analysis. Missing sensed glucose values will be interpolated for up to 30 min segments. Longer periods of missing data will be omitted. If missing data represent >10% of observation time (which will be truncated if a participant leaves the study early), we will examine distributions of other variables in the dataset to see if they differ between those with high/low levels of missingness. We will consider methods to reduce bias in the estimate of treatment effect such as including covariates in the main outcomes model.

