### **Endpoints**

#### **Primary endpoint**

Probability of overnight hypoglycemia. An episode of overnight hypoglycemia is counted if sensor glucose is  $<70$  mg/dL for at least two measurements during an eight-hour period following announced bedtime.

Time frame: The level-one unit of analysis is a single night, and each participant will contribute 27 consecutive nights under each condition.

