## Power analysis

A sample of 20 participants observed for 27 nights in each condition (total number of nights =  $20*27*2 = 1,080$ ) provides >90% power to detect a relative risk (RR) of 0.5 for nights in the intervention period compared to the control period, or >80% power to detect  $RR \leq 0.6$ . This was calculated assuming the risk of 0.09 for overnight hypoglycemia in the intervention period vs 0.18 in the control period (or 0.15 for  $RR=0.6$ ), and an intra-cluster correlation coefficient (ICC) of 0.25. The effect is equivalent to a 50% relative reduction in the likelihood of nocturnal hypoglycemia.

Statistical power for this sample size was calculated by simulating 1,000 datasets with the assumptions above, fitting the mixed effects model, and determining the proportion of those datasets where the p value for the Wald test of the coefficient of the treatment effect was <0.05. Control and intervention proportions were set after reviewing other crossover trials of similar interventions in similar populations.[22], [23] The ICC was determined by drawing samples of

20 individuals/27 nights per person per arm from a combined dataset of nights from the T1D Exercise study T1-Dexi dataset (T1-Dexi is the largest known dataset of physical activity in T1D, a joint effort by The Leona M. and Harry B. Helmsley Charitable Trust, Jaeb Center for Health Research, and the T1-Dexi study group) and a dataset provided to our group at OHSU by Glooko Inc (Mountain View, CA, USA), then calculating the ICC in an unconditional model. An ICC of 0.25 is just below the mean for ICCs calculated over 500 resamples (ICCMEAN = 0.27). In the resampled source data, 85% of participants experienced hypoglycemia on at least one of the 27 sampled nights.

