due to technical problems, the participant may be asked if they can complete additional time in study with the goal to collect at least 2 weeks worth of data in at least one of the arms of the study, such that the participant can be included in the statistical analysis. Additional compensation will be provided for additional time in study. Problems that would qualify for extending the study time are 1) insufficient study supplies requiring the participant to go off of DailyDose + smart snack intervention or to discontinue the control arm for a period of time (such as running out of CGM supplies or bedtime snacks), 2) issues with the smartphone such that DailyDose cannot be used/accessed (such as a due to a damaged phone or problems with the internet connection that prevent data from being uploaded to the remote monitoring system), 3) issues with the CGM system or the capture of the CGM data during the control period or during the intervention period such that DailyDose cannot generate bedtime recommendations due to insufficient CGM data, or 4) scheduling issues such that the participant is unable to complete the control or the DailyDose + smart snack intervention period continuosly. Participants can complete up to 4 additional weeks to make up time the study was paused for technical reasons. Repeating the study time will be optional. The study team will track when participants extend their study time and the reason and this will be included in the annual report to the FDA.

Table 3: Schedule of Events

 DailyDose abbreviated Dd

 Randomization order abbreviations Control first (CG) Intervention first (IG)

 (CG) only

(IG) only

Collect demographic and other baseline characteristics	X											
UPT if applicable and not done in last 7 days (Point of care)	X	X						X				
Collect blood sample for HbA1c, CBC, CMP, TSH testing	X											
Collect information about medical history	X											
Collect information about concomitant medications	X	X	X	X	X	X	X	X	X	X	X	
Download participant's glucose sensor	X											
Complete 3 surveys	X					X 					X 	
Randomization		X										
Collect data on Adverse Events		X	X	X	X	X	X	X	X	X	X	
Train participants on the study procedures to do at home		X					X					
Train participants on use of Dexcom G6 CGM system with G6 and Clarity apps		X 					X 					
Train participants on use of Apple Watch		X										

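### The 14-night inclusion rule discards randomised participants with usable nights in both arms, and make-up time is aimed at the same one-arm floor

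*Combined protocol and SAP*

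**What the plan says.** The Missing data section sets the analysis population: "Participants who contribute at least 14 nights plus 24 hours following bedtime in at least one of the study conditions will be included". The threshold has to be met in one condition only, and no minimum is set for the other.

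The Study Completion session section allows extra time after a technical, supply or scheduling interruption, "with the goal to collect at least 2 weeks worth of data in at least one of the arms of the study", and gives the reason: "such that the participant can be included in the statistical analysis". The allowance is optional and capped: "Participants can complete up to 4 additional weeks to make up time the study was paused for technical reasons".

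The design assumes much more than this floor. Under Primary endpoint, "each participant will contribute 27 consecutive nights under each condition", and the Power analysis rests on "A sample of 20 participants observed for 27 nights in each condition". Statistical analysis methods specifies a mixed model with treatment, sequence, period and a participant random intercept; a random treatment slope is optional. No section adds a both-arm requirement or makes an exception for participants who have nights in both arms but fewer than 14 in each.

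**The concern.** In a 2x2 crossover with a participant intercept, the treatment coefficient is estimated almost entirely from each person's own contrast between conditions. The inclusion rule counts nights in the better-filled arm and ignores whether a contrast exists. A participant with 26 nights split 13 and 13 has a full contrast and is excluded. A participant with 14 nights in one arm has none and is included.

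Two things are at stake. First, randomised data that the model could use are thrown away on a criterion known only after randomisation. Second, the make-up goal can be met without improving the comparison. Someone with 14 control nights and an interrupted intervention period has already reached it, so the stated goal gives no reason to collect the nights that would be worth most.

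**Working it through.** **Inputs.** From Power analysis: 20 participants, 27 nights per condition, ICC 0.25, risks 0.09 vs 0.18 (RR 0.5) or 0.09 vs 0.15 (RR 0.6). From Statistical analysis methods: the model above and a Wald test at p < 0.05, taken as two-sided. From Randomization: 1:1 allocation to sequence. Assumed here: the number of participants who fall short, since the documents give no dropout rate.

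**1. The plan's power.** Linear approximation for RR 0.6: mean binomial variance (0.15×0.85 + 0.09×0.91)/2 = 0.1047; within-person part 0.75×0.1047 = 0.0785; SE = √(2×0.0785/540) = 0.01705; z = 0.06/0.01705 = 3.518; power = Φ(3.518 − 1.96) = 94.0%. For RR 0.5 the same steps give 99.9%. A simulation of 1,000 datasets with a random-intercept logistic model (ICC on the latent scale, risks read as marginal) gives 88.9% and 99.6%. Both methods agree with the stated >80% and >90%.

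**2. Information from one added participant.** A completer's within-person difference has variance 2σ²/27, where σ² is the within-person variance. The treatment estimate is half the difference between the two sequence means, so with n₁ and n₂ completers per sequence

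Var = ¼ × (2σ²/27) × (1/n₁ + 1/n₂), and information = 54 / [σ²(1/n₁ + 1/n₂)].

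Set total variance to 1, so σ² = 0.75 and 54/0.75 = 72. Start from 19 completers (10 and 9): 72/(1/10 + 1/9) = 341.05.

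- Add 27+27: 72/(1/10 + 1/10) = 360.00, a gain of 18.95.
- Add 13+13, which counts as 13/27 = 0.481 of a completer: 72/(1/10 + 1/9.481) = 350.42, a gain of 9.37, or **49.4%** of a completer.
- Add 14+0, by generalised least squares for the full model: a gain of 0.83, or **4.4%**.

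The excluded participant is worth 9.37/0.83, about 11 times the included one. Over assumed ICCs from 0.10 to 0.40, the 14+0 share runs from about 10% down to 2.4%, and the 13+13 share stays at 49.4%. With an assumed random treatment slope (variance 0.05 of unit total variance, ICC 0.25), 13+13 gives 65%, and a one-arm participant gives 2% (control only) to 16% (intervention only).

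**3. What the rule itself costs.** The right comparison is 13+13 participants dropped versus kept. Effective completers m = 4n₁n₂/(n₁+n₂), with each 13+13 participant counted as 0.481; the SE relative to full data is √(20/m).

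| Assumed at 13+13 | Handling | n₁, n₂ | m | SE ratio | Linear power, RR 0.6 |
|---|---|---|---|---|---|
| 3 of 20 | dropped | 8, 9 | 16.94 | 1.087 | 89.9% |
| 3 of 20 | kept | 8.963, 9.481 | 18.43 | 1.042 | 92.2% |
| 5 of 20 | dropped | 7, 8 | 14.93 | 1.157 | 86.0% |
| 5 of 20 | kept | 8.444, 8.963 | 17.39 | 1.072 | 90.7% |

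On the logistic scale, 88.9% corresponds to z = 1.221 + 1.96 = 3.181. Dividing by 1.087 and 1.042 gives 83.3% and 86.3% for 3 of 20. For 5 of 20, direct simulation gives 76.9% dropped and 82.6% kept (simulation error about 1.3 points each). The cost is thus 2 to 3 points for 3 of 20, and 5 to 6 points for 5 of 20.

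**4. One-arm participants.** With 3 of 20 at 14+0, the SE ratio is 1.083 if they are kept and 1.087 if dropped. With 5 of 20, simulated power is 77.3% and 76.9%, which is within simulation error. Keeping them neither harms nor much helps.

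**The case against.** The best defence is that the exclusion is narrow. Only a participant below 14 nights in both arms is lost, meaning about half or more of each 27-night period is missing. Participants with 14+13 or 20+5 nights qualify, and nothing says that the shorter arm's nights are then set aside. A shortfall with a technical cause can be made up over as many as 4 weeks, and up to 3 participants can be replaced. The make-up goal is a floor: it does not require make-up to stop once one arm reaches 14, and extra time may go to either arm. All of this stands and limits the size of the problem. It does not explain why a participant with a usable contrast should be excluded.

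Three stronger readings are tempting and are not supported.

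- A reader might infer that including one-arm participants is an error. It is not. They add a little information on treatment and help to estimate the variance components. Control-only nights also serve the prediction-accuracy endpoint, and intervention-only nights serve the compliance analysis.
- A reader might charge the rule with the whole loss when participants end at 14+0. That loss comes from the missing second-arm nights, and no inclusion rule recovers it.
- A reader might conclude from 76.9% that the trial is underpowered or its power statement wrong. The count of 5 is an assumption, and the stated power is for complete data, where it reproduces.

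Nor is bias demonstrated. Some qualifying interruptions, such as app failure or running out of snacks, arise only under the intervention, so selection related to treatment is possible. The documents give no basis for sizing it.

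**Conclusion.** The point holds in a limited form. As written, the rule excludes a 13+13 participant worth about 49% of a completer and admits a 14+0 participant worth about 4%; the fault lies in the exclusion. The make-up goal repeats the one-arm threshold and so is not tied to what the within-person comparison needs.

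The consequence shown is a modest loss of precision. It rests on the plan's ICC of 0.25, a random-intercept model and an assumed number of affected participants; if nobody falls below 14 nights in both arms, the inclusion rule costs nothing. The correction is worth making because it is cheap and, with 20 participants, there is little information to spare.

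**What to change.** **Missing data section.** Include in the primary mixed model every randomised participant with at least one evaluable night in either condition, with no per-participant minimum. Define an evaluable night, which the section does not do, and clarify what the added 24 hours following bedtime requires. Keep the 14-night criterion only for a sensitivity analysis, restated as at least 14 nights in both conditions.

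**Study Completion session section.** Restate the make-up goal as at least 14 nights in each arm, within the existing optional allowance of up to 4 weeks. Give priority to the arm with fewer nights where the participant is still in that period. Code any make-up nights done after crossover by the period in which they actually occur; the model has only periods 1 and 2, so the SAP should say how such nights enter it.

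**Cost.** Mostly wording. Participants with few nights add somewhat noisier data, which the model weights accordingly. There may be some additional make-up weeks at the existing $40 per week. Make-up time cannot help where a participant has withdrawn.

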## Appendix A: Devices

### Apple Watch

### Apple iPhone

**Dexcom G6 Continuous Glucose Monitoring System which includes Sensor and Sensor Transmitter**

### Scale

**Appendix B: Hypoglycemia Awareness questionnaire:** This survey item will be used to categorize awareness or having reduced awareness of hypoglycemia.

1. Check the category that best describes you: (check one only)

I always have symptoms when my blood sugar is low (A)

I sometimes have symptoms when my blood sugar is low (R)

I no longer have symptoms when my blood sugar is low (R)

2. Have you lost some of the symptoms that used to occur when your blood sugar was low?

Yes (R)

No (A)

3. In the past 6 months how often have you had moderate hypoglycemia episodes? (Episodes where you might feel confused, disoriented, or lethargic and were unable to treat yourself).

Never (A)

Once or twice (R)

Every other month (R)

Once a month (R)

More than once a month (R)

4. In the past year, how often have you had severe hypoglycemia episodes? (Episodes where you were unconscious or had a seizure and needed glucagon or intravenous glucose?)

Never (A)

1 time (R)

2 times (R)

3 times (R)

4 times (R)

5 times (R)

6 times (R)

7 times (R)

8 times (R)

9 times (R)

10 times (R)

11 times (R)

12 or more times (R)

5. How often in the last month have you had readings < 70 mg/dl with symptoms?

Never

1 to 3 times

1 time/week  
2 to 3 times/week  
4 to 5 times/week  
Almost daily

6. How often in the last month have you had readings < 70 mg/dL, without symptoms? R: 5<6,  
A: 6<5;

Never  
1 to 3 times  
1 time/week  
2 to 3 times/week  
4 to 5 times/week  
Almost daily

7. How low does your blood sugar need to go before you feel symptoms?

60-69 mg/dL (A)  
50-59 mg/dL (A)  
40-49 mg/dL (R)  
< 40 mg/dL (R)

8. To what extent can you tell by your symptoms that your blood sugar is low?

Never (R)  
Rarely (R)  
Sometimes (R)  
Often (A)

### Appendix C: Diabetes Distress Scale

Directions: Living with diabetes can sometimes be tough. There may be many problems and hassles concerning diabetes and they can vary greatly in severity. Problems may range from minor hassles to major life difficulties. Listed below are 17 potential problem areas that people with diabetes experience. Consider the degree to which each of the 17 items may have distressed or bothered you DURING THE PAST MONTH and circle the appropriate number.

Please note that we are asking you to indicate the degree to which each item may be bothering you in your life, NOT whether the item is merely true for you. If you feel that a particular item is not a bother or a problem for you, you would circle "1". If it is very bothersome to you, you might circle a "6".

[figure not shown]
I am.....	Not a problem	A slight problem	A moderate problem	Somewhat serious problem	A serious problem	A very serious problem
1. Feeling that diabetes is taking up too much of my mental and physical energy every day.	1	2	3	4	5	6
2. Feeling that my doctor doesn't know enough about diabetes and diabetes care.	1	2	3	4	5	6
3. Feeling angry, scared and/or depressed when I think about living with diabetes.	1	2	3	4	5	6
4. Feeling that my doctor doesn't give me clear enough directions on how to manage my diabetes.	1	2	3	4	5	6
5. Feeling that I am not testing my blood sugars frequently enough.	1	2	3	4	5	6
6. Feeling that I am often failing with my diabetes regimen.	1	2	3	4	5	6
7. Feeling that friends or family are not supportive enough of my self-care efforts (e.g., planning activities that conflict with my schedule, encouraging	1	2	3	4	5	6

me to eat the “wrong foods”).						
8. Feeling that diabetes controls my life.	1	2	3	4	5	6
9. Feeling that my doctor doesn't take my concerns seriously enough.	1	2	3	4	5	6
10. Not feeling confident in my day-to-day ability to manage diabetes.	1	2	3	4	5	6
11. Feeling that I will end up with serious long-term complications, no matter what I do.	1	2	3	4	5	6
12. Feeling that I am not sticking closely enough to a good meal plan.	1	2	3	4	5	6
13. Feeling that friends or family don't appreciate how difficult living with diabetes can be.	1	2	3	4	5	6
14. Feeling overwhelmed by the demands of living with diabetes.	1	2	3	4	5	6
15. Feeling that I don't have a doctor who I can see regularly about my diabetes.	1	2	3	4	5	6
16. Not feeling motivated to keep up my diabetes self-management.	1	2	3	4	5	6
17. Feeling that friends or family don't give me the emotional support that I would like.	1	2	3	4	5	6

**Appendix D: Sleep quality Scale[24]****INSTRUCTIONS:**

- *The following question refers to your overall sleep quality for the **majority** of nights in the **past 7 days ONLY**.*
- *Please think about the quality of your sleep **overall**, such as how many hours of sleep you got, how easily you fell asleep, how often you woke up during the night (except to go to the bathroom), how often you woke up earlier than you had to in the morning, and how refreshing your sleep was.*

1. During the **past 7 days**, how would you rate your sleep quality overall?  
(Please mark only **1** box)

## Appendix E: Study completion interview script

### Questions:

1. What did you call the app?
2. General understanding of app
  - a. If you were telling someone else about the app, how would you describe it?
  - b. What do you think is the best feature of the app?
  - c. What were the positives and negatives of the app?
3. Expectations of the app
  - a. What were your expectations of the system before you started the trial?
  - b. Do you think predicting nighttime lows and providing snack recommendations would help you with diabetes management?
  - c. Did anything surprise you about the app?
4. Usability of the app
  - a. Which of the issues below was the biggest problem during the study?
    - i. The App was confusing to use
      - What were the difficult parts of using the app? Why?
    - ii. The app was visually unappealing
    - iii. The app crashed
    - iv. The app was missing features I consider important
      - What were those features
  - b. Rate the following aspects of the app (scale 1 to 5, 5 is best possible score)
    - i. Stability
    - ii. Navigation
    - iii. Functionality
    - iv. Look and feel
5. Trusting the App
  - a. How easy was it to trust the predictions and recommendations of the app to avoid nighttime low glucose?
  - b. Would you use the app right now to help you avoid nighttime low glucose?
  - c. Would you use the app outside of the study if you could?
6. Barriers to Use
  - a. What might stop you from wanting to use this system in the future if it was available?

